## 4. Endpoints

### 4.1. Primary Endpoint

Successful pre-operative biliary drainage defined as absence of reinterventions for the management of biliary obstructive symptoms.

- For patients undergoing surgery: from stent placement until surgery
- For patients transitioning to palliative management: from stent placement until transition to palliation

### 4.2. Secondary Endpoints

1. Occurrence and severity of adverse events related to the stent and/or stenting procedure
2. Occurrence and severity of surgical complications
3. Occurrence and severity of peri-surgical complications (up to 30 days after surgery)
4. Ability to deploy the stent in satisfactory position across the stricture (Stent Placement Success)
5. Improvement of biliary obstructive symptoms during stent indwell at Week 1 and Monthly until surgery or transition to palliation as applicable, compared to Baseline
6. Improvement of Laboratory Liver Function Tests (LFTs) until surgery for patients undergoing surgery, and at Week 1 and Monthly until transition to palliation, and at 1 year after stent placement for patients not undergoing surgery
7. Biliary Reintervention rate
8. Ability to complete neoadjuvant therapy as intended without stent related interruptions of neoadjuvant therapy
9. Stent migration rate
10. Assessment by surgeon of interference, if any, of SEMS on time to surgery and/or success of pancreaticoduodenectomy
11. For patients transitioning to palliative management: Successful biliary drainage defined as absence of reinterventions for the management of biliary obstructive symptoms from stent placement to 1 year after stent placement

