### 3.1. Scale and Duration

Patients that have gone to surgery will be followed for 30 days post-surgery. For patients that have transitioned to palliation, the Long Term Follow-Up Visit will occur one (1) year after initial treatment. Patients that have not gone to surgery and have not transitioned to palliation (with or without Neoadjuvant Therapy) will be followed up to 1 year post-stent placement. There will be 6-12 participating centers with anticipated enrollment of 122 patients.

At each investigational center, there will be one principal investigator (PI) who will be an endoscopist. Where possible at least one co-investigator should be a pancreaticobiliary surgeon.

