## 9. Potential Risks and Benefits

### 9.1. *Anticipated Adverse Device Effects*

The following anticipated adverse device effects (ADE) should be reported only if they are related to the stent and/or stenting procedure. They have been identified for the WallFlex Biliary FC and UC Stent, as indicated in the commercial Directions for Use (DFU) and may include, but are not limited to:

- Pain
- Bleeding
- Fever
- Nausea
- Vomiting
- Infection
- Inflammation
- Recurrent obstructive jaundice
- Stent occlusion
- Tumor overgrowth around ends of stent
- Tumor ingrowth through the stent
- Mucosal hyperplasia
- Cholangitis
- Cholecystitis
- Pancreatitis
- Ulceration of duodenum or bile duct
- Perforation of duodenum or bile duct
- Stent migration
- Death (other than that due to normal disease progression)
- Stent misplacement
- Perforation of the gallbladder due to the stent covering the cystic duct
- Stent Fracture
- Hepatic abscess

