### **10.2. Relationship to Study Device(s)**

The Investigator must assess the relationship of the AE to the study device as related or unrelated. Unrelated AEs will not be reported. Per protocol, only complications related to stent and/or stenting procedures will be reported. See criteria in **Table 5**.

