### **10.3. *Investigator Reporting Requirements***

Investigators will be required to report all SAEs and ADEs.

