#### **10.3.1. Serious Adverse Events**

These events should be reported to the Sponsor **within 2 business days** of first becoming aware of the event. Events should be documented in the eCRF and all relevant source documentation for the event should be provided to the Safety Trial Manager, as applicable.

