#### **10.3.2. Adverse Events**

Device-related events should be reported to the Sponsor **within 10 business days** of first becoming aware of the event. Unrelated AEs will not be collected.

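### Endpoint 1 counts only events the investigator calls related, and non-serious events called unrelated are not collected, so attribution that differs by arm could bias the safety comparison and be checked only in part

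*Protocol*

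**What the plan says.** Protocol 4.2, item 1, and SAP 5.1, item 1, define the endpoint as "Occurrence and severity of adverse events related to the stent and/or stenting procedure".

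**Who decides.** Protocol 10.2 states: "The Investigator must assess the relationship of the AE to the study device as related or unrelated". Under 3.1, at each centre "there will be one principal investigator (PI) who will be an endoscopist". Table 5 makes the call a judgement of relative likelihood, and an equally likely alternative cause still counts as related. Table 5 is worded around the product, whereas the endpoint also covers the stenting procedure. No masking is described. An independent data review board appears only in the abbreviation list.

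**What happens to unrelated events.**
- 9.1: the anticipated device effects "should be reported only if they are related to the stent and/or stenting procedure".
- 10.2: "Unrelated AEs will not be reported".
- 10.3.2: "Unrelated AEs will not be collected".

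**Text pointing the other way.**
- 10.3: "Investigators will be required to report all SAEs and ADEs".
- 10.3.1, on serious events: "Events should be documented in the eCRF and all relevant source documentation for the event should be provided".
- Appendix B.5.2 makes the investigator responsible for recording, reporting and assessing all adverse events.

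**Data with no relatedness filter.** Reinterventions with their reason (7.8), obstructive symptoms and liver tests at follow-up (7.7), and stent migration (4.2, item 9).

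**The concern.** A relatedness call is usually a label on a recorded event, so a later analysis can ignore it or re-examine it. Under 9.1, 10.2 and 10.3.2 it instead decides whether a non-serious event is recorded at all. Tumour and neoadjuvant therapy are rival explanations for many biliary events in these patients, so there is room for judgement. The endoscopist who placed the stent knows its type; that is an inference, but a safe one when no masking is described.

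The plan also contains expectations that differ by stent. Section 8.1 anticipates more migration with the Fully Covered stent. The sample-size sections allow for endoscopists choosing the Uncovered stent because of where the stricture meets the cystic duct. None of this shows that attribution will differ by arm, but it makes the possibility foreseeable.

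At stake is the by-arm safety table that will be read beside a non-inferiority result. SAP 5.8 carries the same filter: its group of subjects without adverse events would in practice include those whose events were called unrelated.

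**Working it through.** **1. How far the filter reaches**

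| Event | 9.1, 10.2, 10.3.2 | 10.3, 10.3.1 | B.5.2 |
|---|---|---|---|
| Non-serious, called related | recorded | recorded | recorded |
| Non-serious, called unrelated | not recorded | not required | recorded |
| Serious, called unrelated | not reported under 10.2, which makes no exception | recorded in the eCRF | recorded |

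If the conflict is settled in favour of 10.3, the loss is confined to non-serious events called unrelated. If it is settled in favour of B.5.2, nothing is lost from the database. In either case endpoint 1 still counts only related events, and the SAP plans no table that sets attribution aside.

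**2. Size of a possible effect**

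The plan gives no event rate, attribution rate or power for endpoint 1, so there is no figure to reproduce. The one plan input is enrolment: 102 × 1.2 = 122.4, stated as 122, or 122 / 2 = 61 per arm. Everything else below is assumed.

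Formula: recorded rate = true rate × share called related. Arms are Fully Covered (FC) and Uncovered (UC).

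Low rates, equal in truth:
- True 5%: 0.05 × 0.90 = 4.5% versus 0.05 × 0.60 = 3.0%, ratio 1.5. At 61 per arm this is 2.7 versus 1.8 patients.
- True 10%: 0.10 × 0.90 = 9.0% versus 0.10 × 0.75 = 7.5%, ratio 1.2. At 61 per arm this is 5.5 versus 4.6 patients.

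The gap is 61 × 0.015 = 0.9 patient in both cases. Summing exactly over binomial outcomes, a two-sided Fisher test reaches p ≤ 0.05 in 1.1% and 2.4% of such trials. Equal recorded rates of 5% and 10% give 1.1% and 2.2%, so at these rates the distortion would almost never look significant.

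Higher rates (any counted event), same method, 61 per arm:

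| True FC / UC | Share called related FC / UC | Recorded FC / UC | Fisher p ≤ 0.05 |
|---|---|---|---|
| 30% / 30% | 100% / 100% | 30% / 30% | 3.1% |
| 30% / 30% | 90% / 70% | 27% / 21% | 8.2% |
| 30% / 30% | 90% / 50% | 27% / 15% | 28.9% |
| 50% / 50% | 100% / 100% | 50% / 50% | 3.7% |
| 50% / 50% | 90% / 70% | 45% / 35% | 15.9% |
| 50% / 50% | 90% / 50% | 45% / 25% | 57.1% |
| 40% / 20% | 100% / 100% | 40% / 20% | 61.1% |
| 40% / 20% | 50% / 90% | 20% / 18% | 3.5% |

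With equal shares of 80% and equal true rates of 30% or 50%, the figure is 3.0% or 3.3%, so incomplete attribution that is the same in both arms creates no false difference. The SAP specifies no test for endpoint 1; Fisher's test serves here only as a yardstick.

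**The case against.** The case against is substantial, and most of it stands as a limit on the point.

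- **Serious events.** Appendix B.11 requires more than one night in hospital for pancreatitis and emergency gallbladder removal for cholecystitis. Events at that grade would mostly meet the serious-event definition and, if 10.3 governs, reach the eCRF whatever the attribution. That stands. It does not make them count in endpoint 1 when called unrelated.
- **Table 5 favours relatedness in a tie.** This narrows the room for bias but does not remove the judgement.
- **The arm-specific expectations are thin.** The 9.1 list is stated for both stents, and migration has its own endpoint without a filter. So differential attribution is a risk and has not been shown.
- **Commercial devices.** Collecting only device-related events is an explicit choice for marketed stents. That is a fair reason to keep any added collection short.

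A reader might infer that unrelated events are never collected and that no later analysis could detect the problem. The documents do not support either. Sections 10.3 and 10.3.1 and Appendix B.5.2 require more than 10.2 and 10.3.2 allow, and reinterventions, symptoms, liver tests, migration and monitored source records permit some checking. They do not restore non-serious diagnoses that were never entered.

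**Conclusion.** The point holds in limited form. Endpoint 1 rests on an investigator's relatedness call with no masking or adjudication described. Under 9.1, 10.2 and 10.3.2, non-serious events called unrelated are lost, so differential attribution could be checked only in part. The contradiction with 10.3 on serious events and with B.5.2 on all events must be reconciled.

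The size is unknown. At assumed true rates of 5% to 10% it is about one patient at 61 per arm. The larger effects in the table need both higher event rates and wide gaps in attribution, neither of which the documents supply. It would be wrong to read the plan as showing that the safety comparison is biased: bias requires attribution to differ by arm, and there is no evidence that it will. The change is worth making because it is cheap and lets the question be examined for the diagnoses that matter most.

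**What to change.** **Protocol 9.1, 10.2 and 10.3.2.** Require a closed list of diagnoses already named in 9.1 to be recorded whatever the attribution, with relatedness kept as a field:
- cholangitis, cholecystitis, pancreatitis and hepatic abscess;
- perforation of the duodenum, bile duct or gallbladder;
- bleeding that meets the B.11 definition;
- stent occlusion.

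The recording window runs from the first attempt at stent placement until surgery, transition to palliation or end of study, whichever comes first. Leave out pain, fever, nausea and vomiting: the symptom assessments already cover right upper quadrant pain, fever or chills, and nausea or vomiting, and adding them would bring in much non-specific data. Other non-serious unrelated events can stay uncollected. Reconcile 9.1, 10.2 and 10.3.2 with 10.3 and B.5.2 so that the rule for serious events is stated once.

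**SAP 5.1.** Tabulate these diagnoses and all serious events by arm twice over that same window: regardless of attribution, and restricted to those called related.

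**Cost.** Wording changes and a few extra eCRF entries, with no added visit, test or staff. Reported rates will be somewhat higher and will include some events caused by tumour or chemotherapy in both arms. Ascertainment itself stays unmasked.

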## 5. Patient Selection

### 5.1. Inclusion Criteria

Patients who meet all of the criteria listed below (see Table 1) may be given consideration for inclusion in this clinical investigation, provided no exclusion criterion (see Table 2) is met.

**Table 1: Inclusion Criteria**

Clinical Inclusion Criteria	
 
1. Age 18 or older
 
2. Patient indicated for biliary metal stent placement for the treatment of jaundice and/or cholestasis
 
3. Willing and able to comply with the study procedures and provide written informed consent to participate in the study
 
4. Suspicion of pancreatic adenocarcinoma
 
5. Likely indicated for neoadjuvant treatment
 
6. Distal biliary obstruction consistent with pancreatic cancer
 
7. Location of distal biliary obstruction such that it would allow the proximal end of a stent to be positioned at least 2 cm from the hilum
 
8. Endoscopic and surgical treatment to be provided at the same institution
 

-----------------------------	---

### 5.2. Exclusion Criteria

Patients who meet any one of the following criteria (See Table 2) will be excluded from this clinical study.

**Table 2: Exclusion Criteria**

Clinical Exclusion Criteria	
 
1. Benign biliary strictures
 
2. Malignancy secondary to Intraductal Papillary Mucinous Neoplasm
 
3. Surgically altered anatomy where ERCP is not possible
 
4. Previous biliary drainage using a SEMS or multiple plastic stents
 
5. Contraindications for endoscopic techniques
 
6. Patients who are currently enrolled in another investigational trial that would directly interfere with the current study
 
7. Pregnancy
 

-----------------------------	--

## 6. Study Devices

The WallFlex Biliary RX Fully Covered stent and the WallFlex Biliary RX Uncovered stent will be used for the treatment of patients.

The WallFlex Biliary RX Fully Covered and the WallFlex Biliary RX Uncovered Stent Systems are indicated for use in the palliative treatment of biliary strictures produced by malignant neoplasms and relief of malignant biliary obstruction prior to surgery; the WallFlex Biliary RX Fully Covered Stent System is also indicated for use in the palliative treatment of biliary strictures produced by malignant neoplasms and treatment of benign biliary strictures, per CE Mark. For a detailed description of the WallFlex Biliary Stent Systems, please reference the Directions for Use (DFU) included in each device package.

Investigators should use the WallFlex Biliary RX Fully Covered and Uncovered Stent Systems in accordance with the DFUs.

Study devices are labeled on the box and inner pouch and contain information including but not limited to: device name and dimensions, lot number, expiration date, name of legal manufacturer, and investigational use statement. Device labeling will be provided in local language(s) as per national regulations.

Study devices will be available in the following dimensions:

WallFlex Biliary RX Stent	Diameter	Length	Delivery System Diameter	Guidewire Diameter
Uncovered	8 mm	40, 60, 80mm	8 Fr	.035"
	10 mm	40, 60, 80mm		
Fully Covered	8 mm	60, 80mm	8.5 Fr	.035"
	10 mm	40, 60, 80mm		

Stent placement should be such that the proximal end of the stent is minimum 2 cm from the hilum. Performing a biliary or pancreatic sphincterotomy or enlarging a prior sphincterotomy will be done at the discretion of the endoscopist. Per literature, it is recommended that the shortest length of stent required to bridge the stricture is used so as to leave enough of the normal bile duct above the stent available for subsequent anastomosis. It is hence anticipated that SEMS of 80 mm length will rarely or never be selected in this trial.

In case of a failed stent placement due to a device event, a new attempt to place a stent will be made. If a stent placement is not possible due to non-device related reasons (such as inability to cannulate the CBD or reach the papilla, extensive tumor growth at site of papilla, etc.), interventional radiologic (IR) access is allowed and, where possible, should be associated with placement of a study stent over a transhepatically inserted guide-wire in a "rendez-vous"

14 SEP 2015

FINAL

Boston Scientific  
Pre-operative Biliary SEMS  
RCT During Neoadjuvant Therapy  
90905950/Ver AE  
Page 16 of 43

procedure. Percutaneous transhepatic cholangiography (PTC) and a subsequent internal drainage with a stent placement may be done at the same time (one-stage procedure), or PTC with external drainage may be performed 2-3 days before stent insertion (two-stage procedure) per standard of practice. If access to the biliary tree or endoscopic placement of the study stent through a “rendez-vous” procedure fails and patient requires percutaneous transhepatic biliary drainage (PTBD), then the patient will exit the study. In case of failure of SEMS functionality during the neoadjuvant therapy, a new investigational SEMS may be placed, covered or uncovered at the discretion of the investigator. In case of failure of SEMS functionality after transition to palliation, no new investigational SEMS will be provided and patient should be treated per standard of practice.

## 7. Study Visits

### 7.1. Visit Schedule

The schedule of observations and assessments to take place during the study is shown in Table 3 below.

Table 3. Study Event Schedule

Procedure/Assessment	Screening	Baseline	Stent Placement Procedure Visit	Pre-Operative Follow-Up Visits		Biliary Reintervention	Curative Intent Surgery	Transition to Palliative Management Visit	Post-Operative Follow-Up Visit - 30 days from surgery ( $\pm 15$ Days) Office Visit	*Long Term Follow-Up Visit ( $\pm 30$ Days)
				Week 1 ( $\pm 2$ Days) Office Visit/ Telephone Interview	Monthly ( $\pm 15$ Days) Office Visit/ Telephone Interview					
ICF	X									
Demographics		X								
Medical history		X								
Collection of Weight		X		X	X					
Assessment of Biliary Obstructive Symptoms			X	X	X		X	X	X	X (if applicable)
Laboratory Liver Function Test (LFTs)		X		X	X			X		X (if applicable)
Imaging a		X								
Tumor Diagnosis, Staging, and Characteristics			X							
Randomization	X									
Stent Details			X			X (if applicable)	X			
Procedure Details			X			X (if applicable)				
Operative Details							X			
Specimen Pathology							X			
Planned Neoadjuvant therapy			X							
Administered Neoadjuvant therapy (if applicable)				X	X		X			

14 SEP 2015  
FINALBoston Scientific  
Pre-operative Biliary SEMS  
RCT During Neoadjuvant Therapy  
90905950/Ver AE  
Page 18 of 43

Procedure/Assessment	Screening	Baseline	Stent Placement Procedure Visit	Pre-Operative Follow-Up Visits		Biliary Reintervention	Curative Intent Surgery	Transition to Palliative Management Visit	Post-Operative Follow-Up Visit - 30 days from surgery ( $\pm 15$ Days) Office Visit	*Long Term Follow-Up Visit ( $\pm 30$ Days)
				Week 1 ( $\pm 2$ Days) Office Visit/ Telephone Interview	Monthly ( $\pm 15$ Days) Office Visit/ Telephone Interview					
Surgical assessment of tumor invasion							X			
Patient's overall health status		X		X		X			X	X
Adverse events and reinterventions						X (as applicable)				
Device Events						X (as applicable)				
Protocol Deviation						X (as applicable)				

a ERCP, CT and/or MRI

\*Long Term Follow-Up Visit: 1 year after initial treatment for patients that have transitioned to palliation or 1 year post-stent placement for patients that have not undergone surgery or transitioned to palliation (with or without Neoadjuvant Therapy)

14 SEP 2015  
FINAL

Boston Scientific  
Pre-operative Biliary SEMS  
RCT During Neoadjuvant Therapy  
90905950/Ver AE  
Page 19 of 43

## 7.2. Screening – *Office Visit*

- Informed Consent
- Eligibility Criteria Assessment
- Randomization

No study-specific testing will be conducted until after the patient has signed an Informed Consent Form. A Screen Failure/Enrolled Log will be maintained in EDC by the center to document select information about candidates who signed consent.

Written Informed Consent must be obtained for all patients who are potential study candidates. Patients will be asked to sign the Informed Consent Form before any study-specific tests or procedures are performed. The Informed Consent Form is study-specific and must be approved by the study Institutional Review Board (IRB). Study personnel should explain that even if a patient agrees to participate in the study and signs an Informed Consent Form, the inclusion/exclusion criteria may demonstrate that the patient is not a suitable candidate for the study. Screening and enrollment information will be collected in the database for all patients who sign a consent form.

## 7.3. Baseline Visit – *Office Visit*

- Demographics
- Medical history
- Collection of Weight
- Patient's overall health status
- Assessment of Biliary Obstructive Symptoms
  - Right Upper Quadrant Pain
  - Fever/Chills
  - Jaundice
  - Itching
  - Dark urine
  - Pale stools
  - Nausea/Vomiting
- Laboratory Liver Function Tests (LFTs)
  - Serum Albumin level
  - Total Bilirubin
  - Alkaline Phosphatase
  - SGPT (ALT)

- Imaging

#### **7.4. *Tumor Diagnosis, Staging, and Characteristics – Office Visit***

- Tumor Diagnosis, Staging, and Characteristics can occur any time between the Screening Visit and the Stent Placement Procedure Visit

#### **7.5. *Planned Neoadjuvant Therapy***

- Planned Neoadjuvant Therapy can occur any time between the Screening Visit and the Stent Placement Procedure Visit

#### **7.6. *Stent Placement Procedure Visit – Office Visit***

- Placement of WallFlex Biliary RX stent(s)
  - During WallFlex Biliary RX placement the stent should be adjusted with the proximal end of the stent no more than 1-2cm beyond the proximal end of the stricture. This favors both stability and homogeneous development of tissue hyperplasia at the proximal uncovered part.
- Procedure Details
- Stent Details
- Adverse Events (as applicable)
- Device Events (as applicable)

#### **7.7. *Pre-Operative Follow-Up Visit – Phone and/or Office Visit***

- Week 1 and Monthly until surgery or transition to palliation as applicable
- Collection of Weight
- Patient's overall health status
- Assessment of Biliary Obstructive Symptoms
  - Right Upper Quadrant Pain
  - Fever/Chills
  - Jaundice
  - Itching
  - Dark urine
  - Pale stools
  - Nausea/Vomiting
- Laboratory Liver Function Tests (LFTs)
  - Serum Albumin level
  - Total Bilirubin
  - Alkaline Phosphatase
  - SGPT (ALT)

- Administered Neoadjuvant therapy
- Adverse events and reinterventions (as applicable)
- Device Events (as applicable)

#### **7.8. *Biliary Reintervention Visit (Arm 1 or 2) – as needed***

- Timing
- Reason for Biliary Reintervention
- Type of Biliary Reintervention (including SEMS placement or removal)
- Adverse Events (as applicable)
- Device Events (as applicable)

